#### **Medical notes check**

The central study team will follow up any complications reported by participants with the local research team at participating sites. Details will be collected and recorded on a complications form.

In addition, a final readmission checklist will be undertaken by the research staff on participating site records at 24 months post-randomisation to ensure that all complications data are collected from all participants (i.e. those who had not returned a questionnaire). Data from any readmission events e.g. revision/further surgery identified will be recorded on the Complications Form.

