## 17.2.3. Follow-up assessments/subsequent visits

Follow-up will involve:

- Participant questionnaires at 6-, 12- and 24-months post randomisation
- Medical notes check (local sites) to record complications
- Appointment for a follow-up CT scan at 24 months post-randomisation for participants who have had LFS only.

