## 20.3. Expected adverse events

Expected events from LFS include intra-operative, early post-operative and post-operative complications. Intra-operative expected events can include excessive bleeding/blood loss, vascular injury, peritoneal tear, dural tear, nerve injury, damage to nerve root, damage to spinal cord, Cauda Equina, visceral injury, bowel injury, screw misplacement, implant malposition, loss of swab, bone fracture, loss of purchase of fixation, wrong level surgery as well any other complications associated with the surgical approach. In addition, General Anaesthetic expected events can include additional intra-operative complications i.e. Anaesthetic complications (aspiration, myocardial infarction, air embolism, cardiac problems and death). Further complication can be systemic such as haemorrhage or the need for further surgery over the 24-month period.

Expected early post-operative and post-operative complications include wound infection, thromboses (DVT and PE), bleeding that requires transfusion, CSF Leak, hematoma or clot formation around the nerve or spinal cord, pseudarthrosis, cage or implant movement or migration, malposition of screws, screw cut out, breakage of screws or rods, construct failure i.e. Implant pullout, Junctional problems i.e.: adjacent segment issues, Cauda Equina syndrome, damage to spinal cord, sympathetic nerve damage, damage to nerve root, damage to major blood vessels, scarring around the nerve, loss of bladder/bowel, paralytic ileus, loss of sensations/motor power to legs, warm legs, worsening pain or symptoms, retrograde ejaculation (men only), sexual dysfunction (male and female). In addition, early post-operative and post-operative risk of complications include: stroke, heart attack, death. General Anaesthetic complications include. brain haemorrhage, ischaemic stroke, subarachnoid haemorrhage.

Expected event from BCC include significant unexpected increase in pain due to unaccustomed new exercise programmes, adverse events associated with prescribed medications, damage to the sciatic nerve, allergic reaction (e.g. to medications), infection.

Any expected adverse events related to the procedures will be collected as complication data on a CRF. The central study team will follow up any complications reported by participants with the local research team at participating sites.

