# 20.4. Reporting of SAEs from sites to the CTU study team

Only serious adverse events considered by the site investigator to be related (possibly, probably, or definitely) to the study intervention will be reported immediately to the central study team. Such events will be reported immediately to the Study Office as follows:

SAEs will be reported by the local site research team using the SAE form within the REDCap study database, within 24 hours of becoming aware of the event. The CTU is automatically notified of the SAE report through the database. A paper SAE form should be used as a back-up if the SAE form is not available electronically. This should be e-mailed to [contact] within 24 hours of becoming aware of the event. The central CTU study team will acknowledge receipt of any SAEs reported via e-mail within one working day and provide the site with a unique SAE Log number.

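### The 24-month back-stop for complications looks only for readmissions in participating-site records, so it cannot ensure complete capture, and the stated collection rule leaves related, non-serious, unlisted events without a clear route

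*Protocol*

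**What the plan says.** Section 9.2 makes complications, including readmissions, an additional outcome under the secondary outcomes. It plans clinician and researcher forms over 24 months for surgical complications and for complications of best conservative care (BCC).

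For follow-up, section 17.2.3 lists a "Medical notes check (local sites) to record complications", with no restriction to readmissions. The Medical notes check part of section 17.3 then describes two steps. Complications reported by participants are followed up with the site. The second step reads: "final readmission checklist will be undertaken by the research staff on participating site records at 24 months post-randomisation to ensure that all complications data". Its stated reach, which singles out non-returners, is this: "collected from all participants (i.e. those who had not returned a questionnaire"). What the second step records is this: "Data from any readmission events e.g. revision/further surgery identified will be recorded on the Complications Form". Section 20.3 repeats the step, and its examples (haematoma evacuation, metalwork revision, wash-out) are all surgical.

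The collection rule is in section 20.3: "Any expected adverse events related to the procedures will be collected as complication data on a CRF". The expected list for lumbar fusion surgery (LFS) is long and contains "warm legs, worsening pain or symptoms, retrograde ejaculation (men only"). The BCC list is short and opens: "Expected event from BCC include significant unexpected increase in pain due to unaccustomed new exercise programmes". Section 20.4 adds: "Only serious adverse events considered by the site investigator to be related (possibly, probably, or definitely) to the study intervention will be reported immediately". Section 22.3 presents adverse events descriptively.

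**The concern.** A step described as ensuring complete data should be able to find the events in question. This one searches for one consequence of a complication (readmission) in one set of records (the participating site's). A wound infection treated in the community, a thrombosis managed as an outpatient or a loss of sensation noted in clinic is a complication under section 20.3 but need not be a readmission.

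The participants for whom the step matters most are those who returned no questionnaire, because the participant-report route is then weak or absent. If LFS complications lead to readmission at the site more often than BCC complications do, the same back-stop recovers different shares in the two arms. The arm-specific wording of the collection rule can act in the same direction.

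At stake is the harm side of a surgery-versus-conservative-care comparison that section 33.2 expects to inform commissioning. Descriptive tables have no model behind them that could correct unequal ascertainment.

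**Working it through.** **1. Stated aim against stated tool**

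| Item | Where | Scope |
|---|---|---|
| Outcome | 9.2 | Complications, with readmissions as one part |
| Follow-up list | 17.2.3 | Notes check to record complications; no readmission limit |
| Back-stop | 17.3 and 20.3 | Readmission checklist, participating-site records, once at 24 months |
| Claimed result | 17.3 and 20.3 | All complications data, including for non-returners |

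The tool is narrower than the outcome, narrower than the notes check in 17.2.3, and narrower than the claim.

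**2. Source of records**

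Section 10.11 refers to community partners, and section 13.2 allows BCC to vary with local service provision. A harm noted by another provider need not appear in participating-site records. Section 10.10 describes registry and hospital-statistics linkage for long-term outcomes and does not name it as a source for this check.

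**3. Collection rule**

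- A related serious event, listed or not, is reported under 20.4.
- A related, non-serious, listed event is collected under 20.3.
- A related, non-serious, unlisted event has no clearly stated route. The lists are introduced with words such as include, which suggests that they are open. Table 4, however, defines an unexpected event by its absence from the protocol's list, so listing has a consequence.

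**4. Pain wording**

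Relatedness applies to both arms. Beyond that, the LFS list names worsening pain or symptoms with no further qualifier. The BCC entry requires the increase to be significant, unexpected and due to a new exercise programme. Section 13.2 also offers manual therapy and radiofrequency denervation, and increased pain after either is not named. Thromboses, stroke and heart attack appear by name only on the LFS list.

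**5. Illustration of size (assumptions, not estimates)**

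The sample size reproduces. A difference of 8, SD 18, two-sided 5% and 90% power with a t-test need 107.4, so 108 per arm, and 108/0.80 = 135 per arm, 270 in total. The allowance for loss is therefore 0.20 × 135 = 27 per arm.

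The protocol gives no complication or readmission rates. Let d be the share of an arm that returns no questionnaire and r the share of their complications that lead to readmission at the site. Assume complete capture in returners and no other route for non-returners:

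capture = (1 − d) + d × r

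| d | r = 0 | r = 0.5 | r = 1 |
|---|---|---|---|
| 5% | 95% | 97.5% | 100% |
| 10% | 90% | 95% | 100% |
| 20% | 80% | 90% | 100% |

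For equal true rates, the LFS/BCC ratio of captured events would be:

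- d = 20% in both arms and equal r: 1.00.
- d = 20% in both arms, r = 0 in BCC: 0.90/0.80 = 1.13 at r = 0.5 in LFS, and 1.00/0.80 = 1.25 at r = 1 in LFS.
- d = 10% in LFS and 30% in BCC, r = 0 in BCC: 0.95/0.70 = 1.36 at r = 0.5 in LFS, and 1.00/0.70 = 1.43 at r = 1 in LFS.

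The assumption of no other route is stricter than the protocol, so these figures show direction and mechanism only.

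**The case against.** The strongest reply is that the checklist is an addition to other routes and not the capture system itself. Section 9.2 plans complication forms for both arms. Table 2 schedules complication data and safety reporting at 6, 12 and 24 months. The questionnaires ask about healthcare use (sections 17.2.3 and 23.1), which may bring a treated complication to light. LFS includes a usual post-operative review, BCC staff complete their own forms, and sites report related serious events. This stands, and it rules out several stronger readings.

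- **That complications are under-counted and the arms not comparable.** A reader might infer this as fact. The text shows only that events can be missed. Some difference between the lists is inherent, since screw breakage has no BCC counterpart, and no between-arm test of adverse events is planned.
- **That 27 participants per arm are covered only by the checklist.** The 20% is a sample-size allowance for loss. A participant lost at 24 months may have answered at 6 and 12 months, telephone follow-up is planned, and the other routes remain.
- **That participant reports are entirely unprompted.** The itemised questionnaire list in 17.2.3 has no complications item, but Table 2 has a complication-data row below the questionnaire heading. The CT scan row also sits below it, so the table does not settle the matter either way.
- **That worsening pain counts after LFS unconditionally.** It must still be related to the procedure. Pain and disability are also measured identically in both arms by the monthly pain score and the Oswestry index.
- **That an unlisted event is captured nowhere.** Section 20.3 does not say that only expected events are collected, and the forms in 9.2 carry no such limit.

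What the reply does not remove is the mismatch between the completeness claim and the tool. The BCC data actually described (attendance and an outcome statement in 13.4, types of care and sessions in 17.2.2) do not mention complications.

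**Conclusion.** The point holds in a limited form. As written, the 24-month check can find only readmissions in participating-site records, so it cannot ensure all complications data for participants who returned no questionnaire. Events in that group that reach no clinician form or serious adverse event report can be missed, possibly to a different extent by arm. Separately, section 20.3 leaves the route for related, non-serious, unlisted events unclear and words increased pain more narrowly for BCC than for LFS.

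The number of events affected cannot be derived from the protocol. The illustration rests wholly on assumed non-return and readmission shares, and equal shares in the two arms would give no imbalance. The primary outcome, sample size and power are untouched. The change is worth making because it is cheap and because ascertainment cannot easily be repaired after follow-up ends.

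**What to change.** 1. **Medical notes check (17.3) and its repeat in 20.3.** Make the scheduled 24-month check cover all complications, for every participant in both arms, in the available site records and BCC delivery records. Use the existing Complications Form with readmission as one item, which matches 17.2.3. If this is not feasible, drop the claim that the step ensures all complications data.
2. **Collection rule (20.3).** Collect any adverse event related to the allocated intervention, whether listed or not. Keep the expected lists for judging expectedness of serious events. Use the same wording for increased pain in both arms.
3. **Questionnaire list (17.2.3) and Table 2.** Reconcile the two so that the 6-, 12- and 24-month questionnaires include a complications prompt.

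The cost is protocol wording, one questionnaire item if none exists, somewhat more site time per participant at a check that is already planned, and more non-serious events to code.

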#### CT scan appointment

For participants who have undergone lumbar fusion surgery an appointment for a follow-up CT scan will be planned at the 24 months follow-up timepoint as part of the fidelity assessment of the LSF (to determine if there is evidence of bony fusion in the lumbar spine).

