#### 9.2. Primary and secondary objectives and outcome measures

The primary outcome is the Oswestry Disability Index (ODI), a validated LBP physical function disability score, at 24 months (also measured at 6 & 12 months). The ODI is well validated and a commonly used outcome measure in LBP RCTs including surgery and contains 10 items that assess domains including personal care, walking, standing and sleeping.

Secondary outcomes include LBP severity (Numerical Rating Scale), measured using monthly SMS data or by email or paper options dependant on participant preference (over 24 months). We will also collect participant reported outcome measures reported via questionnaires at 6, 12 and 24 months. The participant questionnaires include: quality of life (EQ-5D-5L), depression (PHQ8), fear avoidance beliefs (TSK), pain self-efficacy (PSEQ), work outcomes (days-off-work), comparison of back pain from entering the study to timepoint of questionnaire using Global Perceived Effect Scale (GPE), healthcare use (NHS and non-NHS including concurrent treatments ie: analgesia) and treatment satisfaction measured at 24 months follow-up with scoring 0-10 (with 10 being very satisfied with treatment).

Further secondary outcome measures will be collected throughout the 24 months using specially designed CRF's to be completed by clinicians and researchers regarding surgery, Best Conservative Care (BCC), Surgery complications (intra and post operative), further surgery including re-admission, Fusion Failure (LFS participants only), BCC complications.

Objective	Outcome measure	Time point(s) of evaluation of this outcome measure (if applicable)
1. To test for superiority of	Primary:	24 months (also measured at 6
lumber fusion surgery (LFS)	LBP-related physical function	& 12 months)
versus BCC on disability	using the Oswestry Disability	
(physical function) in	Index (ODI version 2.1b)	
patients with persistent		
lower back pain (LBP)		
	Secondary:	
2. To investigate the cost-		
effectiveness of LFS	LBP severity (Numerical	
compared with best	Rating Scale) monthly – post	
conservative care (BCC)	randomisation	
	Participant reported	
	outcomes	

	measured at 6m, 12m and	
	24m post randomisation:	
	1. Quality of Life: EQ-5D-5L	
	2. Pain Self-efficacy	
	Questionnaire (PSEQ)	
	3. Patient Health	
	Questionnaire (PHQ8)	
	4. Tampa Scale of	
	Kinesiophobia (TSK)	
	5. Global Perceived Effect	
	Scale (GPE)	
	6. Healthcare Resources	
	Use	
	7. Work status	
	8. Treatment Satisfaction	

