#### 10.9. Central review procedures

Not applicable for this study.

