#### Fidelity of the LFS arm

Issues of adherence and fidelity are more straightforward for LFS (there are no grades of adherence to the surgery), but a different set of fidelity issues exist. A surgical procedure CRF will be included to record what was done at operation. It is also important to ascertain whether lumbar bony fusion has occurred or not, especially for interpretation of trial results. A follow-up CT scan for those who have LFS in the trial, at 24 months post-date of randomisation, will provide these data.

The assessed fidelity will be fed back to sites for the duration of the trial, including evaluation of whether intervention fidelity changes during the trial. This is in keeping with the revised guidelines from MRC on complex healthcare interventions and similar approaches have been utilised elsewhere.

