## 17.3. Communication with study participants by the central study team

At 6-, 12- and 24-months participants will be sent either a postal questionnaire or an email from the central study team with a personalised link asking them to complete the electronic questionnaire, depending on their stated preference. If the paper-based version of the questionnaire is requested, this will be sent to participants to complete and return to the Trial Office in a prepaid envelope.

Reminders will be sent to participants who do not respond to the initial follow up questionnaires by post or email with an electronic link (dependant on participant preference) at 2 weeks and a further 2 weeks later if there is no response. This data would be entered onto the trial database by the data entry personnel at the Trial Office.

Telephone follow-up will be used (2 weeks after), as applicable, to contact those who do not respond to either the initial or reminder questionnaire. Telephone and email follow-up will also be used to collect a core set of questionnaire items for the Oswestry Disability Index questionnaire

(primary outcome), and other outcome data, if these have not been fully completed on the returned questionnaire.

Participants will be contacted with regular newsletters (by email or post) to disseminate study progress and maintain engagement in the study.

Assessments	Screening	Baseline	Intervention LFS/BCC	6months	12months	24months (Primary outcome timepoint)
Eligibility	Х					
Informed Consent		х				
QRI Consent *		Х*				
Demographics		х				
Randomisation		х				
Intervention Details			Х			
Participant Completed Questionna	ires:					-
Oswestry Disability Index (ODI)		х		х	Х	x
Quality of life (EQ-5D-5L)		х		х	Х	х
Depression (PHQ8)		х		х	Х	х
Fear of movement beliefs (TSK)		х		х	Х	х
Pain Self-efficacy (PSEQ)		х		х	Х	x
Global Perceived Effect Scale (GPE)		х		х	Х	x
Healthcare Resource Use				х	х	х
Treatment Satisfaction						x
Work Status		х		х	Х	х
LBP severity (NRS) [over 24 months]		х		х	х	x
Safety reporting				х	Х	x
Complication data				х	Х	x
CT Scan at 24months post randomisation						x
Participant interviews **		X**				

Table 2: Scheduled assessments/outcome collection for the study

\*Optional for integrated information study

\*\* Optional for integrated Information Study

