#### 19. IMAGING

Data will be collected on any MRI, SPECT CT, standing X-Rays and other imaging that has been undertaken in the 12m pre-randomisation.

For participants randomised to the surgery arm they will undergo Image intensification during the surgical procedure.

Standard Computed Tomography (CT) scans for patients randomised to surgery will be carried out at the 24-month follow-up time point as part of the fidelity assessment. The clinical team at the local site will review and complete a CRF to indicate whether spinal fusion was achieved.

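### The fidelity CT in the surgical arm shares the 24-month time point with the self-completed primary ODI and no order is fixed, so some LFS participants could learn their fusion status before they score it

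*Protocol*

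**What the plan says.** Section 9.2 sets the endpoint: "The primary outcome is the Oswestry Disability Index (ODI), a validated LBP physical function disability score, at 24 months (also measured at 6 & 12 months"). Section 17.2.3 has participants complete it by post or online, from a questionnaire sent by the central study team.

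The CT runs on the same clock. Under Fidelity of the LFS arm (13.4): "A follow-up CT scan for those who have LFS in the trial, at 24 months post-date of randomisation, will provide these data". Section 17.2.3 lists "Appointment for a follow-up CT scan at 24 months post-randomisation for participants who have had LFS only". The CT scan appointment text in 17.3 repeats the timing and gives the purpose: "an appointment for a follow-up CT scan will be planned at the 24 months follow-up timepoint as part of the fidelity assessment". Table 2 has a row "CT Scan at 24months post randomisation", marked in the same 24-month column as the ODI, which is the column labelled as the primary outcome time point.

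On reading the scan, section 19 says: "The clinical team at the local site will review and complete a CRF to indicate whether spinal fusion was achieved". Section 10.9, on central review, reads "Not applicable for this study". Table 3 lists site clinical and research staff as not blinded.

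On chasing the questionnaire, 17.3 gives a reminder at 2 weeks, another 2 weeks later, and then: "Telephone follow-up will be used (2 weeks after), as applicable, to contact those who do not respond".

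No section requires the questionnaire to be returned before the scan, gives a scan window, or says whether the participant is told the result.

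**The concern.** The ODI is a subjective score given by someone who knows their allocation. That open-label weakness is unavoidable here and exists from the day of randomisation. The CT can add something different: new, outcome-like information, in one arm only, at the moment the primary outcome is measured. Whether the spine has fused is likely to matter to someone who had the operation. The Protocol itself lists fusion failure among the secondary outcomes (9.2) and pseudarthrosis among the expected complications (20.3).

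If the result reaches a participant before the ODI is scored, any resulting shift enters the LFS minus BCC difference at 24 months, with nothing in BCC to offset it. The other 24-month self-reports (TSK, PSEQ, GPE, treatment satisfaction) would be open to the same influence. Section 13.4 wants fusion status to help interpret the trial results, and that reading is less clean if the label came before the score.

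The order of scan and questionnaire is a matter of trial procedure. It has to be fixed before the first 24-month contacts, because an analysis plan cannot restore it afterwards.

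**Working it through.** **1. Do the facts hold?**

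| Item | ODI | Fidelity CT |
|---|---|---|
| Time point | 24 months from randomisation (9.2, 17.2.3) | 24 months from randomisation (13.4, 17.2.3, Table 2) |
| Who | Both arms | Operated participants (17.2.3, 17.3) |
| Organised by | Central study team (17.2.3, 17.3) | Appointment planned (17.3), scan read by the local clinical team (19) |
| Order relative to the other | Not stated | Not stated |

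One wording needs reconciling: 17.2.3 and 17.3 refer to participants who have had LFS, while section 19 refers to those randomised to surgery. On either wording BCC has no scan.

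**2. How late can an ODI arrive?** First reminder at 2 weeks, second 2 weeks later, telephone contact 2 weeks after that: 2 + 2 + 2 = about 6 weeks after sending. If the telephone step is counted from the first reminder, it is 2 + 2 = 4 weeks. This applies to non-responders only. A scan booked at 24 months could fall inside this period.

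**3. The plan's own sample size.** Inputs from 22.2: difference 8, SD 18, two-sided 5%, 90% power, 20% loss. With the t distribution, 108 per arm gives 90.2% power, and 108 / 0.8 = 135 per arm, 270 in total, as stated. The normal approximation gives 107 per arm, which inflates to 134 per arm and 268 in total. The sample size is sound and this point does not change it.

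**4. Illustrative size of a bias.** Bias = f × d, where f is the share of LFS participants who know the result before scoring and d is their net mean ODI shift. The Protocol gives neither, so both are assumptions: f from 0 to 0.75, d from 0 to 4 points in either direction.

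- Lower end: f = 0 or d = 0 gives 0.
- 0.25 × 2 = 0.5 points; 0.5/8 = 6% of the target.
- 0.5 × 4 = 2 points; 2/8 = 25%.
- Upper end: 0.75 × 4 = 3 points; 3/8 = 38%.

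Zero belongs in the range. News of fusion may lower the ODI and news of non-fusion may raise it, so the two could cancel. No fusion rate is given.

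**5. What such a bias would do.** With 108 analysed per arm, the standard error of the difference is 18 × √(2/108) = 2.449. Let b be the bias. Power, if b works against LFS and the true effect is 8, is Φ((8 − b)/2.449 − 1.96). The error rate when there is no true effect is 1 − Φ(1.96 − b/2.449) + Φ(−1.96 − b/2.449).

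| Net bias (points) | Power if against LFS | Two-sided error under no effect |
|---|---|---|
| 0 | 90.4% | 5.0% |
| 0.5 | 86.5% | 5.5% |
| 1 | 81.5% | 6.9% |
| 2 | 68.8% | 12.9% |
| 3 | 53.2% | 23.2% |

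These use the normal approximation, hence 90.4% rather than 90.2% in the first row. They show how sensitive an 8-point comparison is to small shifts. They do not predict a shift.

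**The case against.** The strongest reply is that the link from scan to bias is not in the document. The scan must be done, read and disclosed before the ODI is scored. The Protocol describes a fidelity scan and a form completed by the local team, with no results visit. A reader might infer that participants will be told their fusion status. The text does not support that: it is silent both on telling and on withholding. What stands is that nothing prevents disclosure first.

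A reader might also infer that any shift could never be told apart from the effect of surgery. That goes too far. The primary model (22.3) includes a treatment-by-time interaction, and the 6- and 12-month ODI precede this CT, so an abrupt late change would be visible. This is a partial check only. Section 9.3 chose 24 months partly because of waiting lists, so a late change could also be genuine.

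It is tempting to add that the extra hospital visit would raise questionnaire return in LFS alone. Nothing supports this. The reminders and telephone calls in 17.3 and the vouchers in section 30 are the same for both arms.

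Three further points are fair:

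- Prompt responders are exposed only if scanning, reading and disclosure all come before their reply, so the 6-week chase concerns late responders.
- LFS already includes intra- or postoperative x-rays and a usual review (13.1), so operated participants may already have imaging feedback that BCC participants lack.
- Section 13.1 leaves the checking of LFS fidelity to be finalised in the internal pilot. The order could still be settled there, well before the first 24-month scan. That leaves time for the fix, but no section commits to fixing the order.

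**Conclusion.** The point holds as a gap in procedure. The one-arm fidelity CT and the self-reported primary outcome share a time point, the scan is read by unblinded local staff, and neither the order nor disclosure is controlled. Some LFS participants could therefore score the ODI knowing their fusion status.

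How much this matters cannot be derived from the Protocol. The illustrative 0 to 3 points, in either direction, rests wholly on assumed values of f and d, and zero is a legitimate value. It should not be read as an estimate of bias, nor as showing that the primary comparison is invalid. The case for acting is that the exposure is avoidable, falls in one arm, coincides with the primary measurement and costs little to remove. The change should be made, though the trial does not depend on it.

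**What to change.** In 17.2.3, 17.3 (CT scan appointment) and 19, state that the study CT for fidelity is done after the participant's 24-month ODI is logged as received, or after the reminder and telephone chase has closed, whichever comes first. State that this does not affect imaging done for clinical need. Record the dates of the 24-month ODI and of the CT, and report how many LFS participants completed the ODI after the scan. While editing, reconcile the scanned population between 17.2.3/17.3 and 19.

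The cost is Protocol and site-instruction wording and a check of ODI receipt before the scan. Section 24.5 already gives sites access to ODIs submitted electronically. Paper and telephone returns are entered centrally (24.6), so sites would need to be told when those arrive. No extra scan is needed. The downside is timing: the scan moves by up to about 6 weeks of chasing plus local booking time, which the Protocol does not quantify, and later appointments might reduce attendance somewhat. Section 20.1 already extends safety reporting to include a period for the 24-month CT but gives no length, so its wording should be made to cover the later scan.
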